Serotype-specific urinary antigen detection (ssUAD) has emerged as a promising non-invasive tool for diagnosing and serotyping pneumococcal pneumonia. The ssUAD test is a 25-plex Luminex-based extended-range urine antigen capture assay developed by UKHSA, which has shown favourable results for diagnosing pneumococcal disease among adult patients in the UK. The 24-serotype-specific urine antigen detection (24ssUAD) assay can detect pneumococcal capsular polysaccharide antigens in urine, offering greater diagnostic sensitivity than the culture-based method. The current version of ssUAD targets 24 pneumococcal serotypes and has a sensitivity of 96.2% and specificity of 89.9% among adults with community-acquired pneumonia or invasive pneumococcal disease in the UK. However, there is limited data on the surveillance and diagnostic performance of ssUAD in high-carriage and disease-burden settings, such as Malawi, where asymptomatic or healthy children may also shed pneumococcal antigens in urine, making it more challenging to distinguish invasive disease. Unpublished data from our testing of the 24ssUAD assay on historical urine samples from Malawian children

MALAWI LIVERPOOL  
WELLCOME PROGRAMME

KAMUZU  
UNIVERSITY  
OF HEALTH SCIENCES

[figure not shown]
with acute respiratory infection (ARI) indicate that pneumococcal antigens can be detected in urine, suggesting the assay's potential utility in such settings and highlighting the need for further evaluation to distinguish between carriage and disease. The data also revealed that pre-hospital antibiotic exposure significantly reduced the sensitivity of culture-based methods, decreasing pneumococcal detection rates from 81% to 21%, highlighting the potential diagnostic advantage of urine antigen assays in such contexts.

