Available evidence primarily comes from adult populations where nasopharyngeal colonisation is relatively uncommon and less likely to interfere with urine-based antigen detection. In contrast, children in sSA, including Malawi, often exhibit high nasopharyngeal carriage rates, which may make it difficult to distinguish between antigenuria due to invasive disease and antigen spillover from asymptomatic carriage.

[figure not shown]
Limited data exist on the specificity of ssUAD in high-carriage paediatric populations, particularly in low-resource settings where distinguishing between pneumococcal disease and antigenuria from asymptomatic carriage remains challenging. As such, there is an urgent need for context-specific data to define serotype-specific thresholds that can accurately differentiate carriage from disease. Addressing this gap is critical for the optimal use of ssUAD in clinical diagnostics, disease surveillance, and vaccine impact evaluations in high-burden LMIC settings.

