#### **1.4.2. Specific objectives**

1. Determine the prevalence of serotype-specific pneumococcal antigens in urine among children under five years of age with pneumonia compared to healthy counterparts.

MALAWI LIVERPOOL  
WELLCOME PROGRAMME

KAMUZU  
UNIVERSITY  
OF HEALTH SCIENCES

2. To characterise the association between the detection of serotype-specific antigens in urine and nasopharyngeal pneumococcal carriage among children.
3. To define revised ssUAD thresholds that distinguish pneumococcal carriage from disease, to support field evaluations and inform diagnostic and surveillance strategies in Malawi and similar settings.

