### **2.6. Sample size:**

The minimum required sample size for this study is 147 urine specimens, accounting for a 10% allowance for non-response or data loss. This estimate is based on detecting a significant difference in pneumococcal serotype-specific antigen detection between children hospitalised with pneumonia, those treated at health centres, and healthy community controls.

[figure not shown]
The core sample size calculation indicates that at least 49 specimens per group are needed, assuming antigen detection rates of 70% in hospitalised children, 53% in health centre cases, and 35% in healthy controls, based on prior studies. Using a two-sided significance level of 0.05 and 80% statistical power, the estimated minimum total sample size is 147 participants across the three groups.

To address the limitation of a small sample size faced in our preliminary analysis of 214 urine specimens from hospitalised children, we plan to test all 350 urine specimens collected under the parent NP Resistome study. This expanded approach will improve the precision of our estimates, allow for subgroup analyses, and provide broader insights into pneumococcal antigen detection patterns across the study groups

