### **2.8.3. Defining diagnostic thresholds (objective 3):**

Signal intensity data (median fluorescence intensity or equivalent) from the 24ssUAD assay will be analysed to compare antigen profiles between cases (pneumonia) and carriers (healthy children). Receiver Operating Characteristic (ROC) curve analysis will be used to define optimal cut-off values for distinguishing pneumococcal disease from carriage. Area under the curve (AUC) values will quantify diagnostic performance. Findings will be cross-referenced with previously published UK datasets to support broader applicability.

All analyses will be conducted using R software, with statistical significance defined at  $p < 0.05$  and confidence intervals at 95%. Graphical data presentation will include bar charts, ROC curves, and stratified prevalence plots.

MALAWI LIVERPOOL  
WELLCOME PROGRAMME

KAMUZU  
UNIVERSITY  
OF HEALTH SCIENCES

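### Section 2.8.3 takes optimal ssUAD cut-offs from the study's own ROC curves and has no step that assesses them on data not used to choose them

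*Protocol*

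**What the plan says.** Section 2.8.3 compares assay signal intensity between children with pneumonia and healthy children. It then says "Receiver Operating Characteristic (ROC) curve analysis will be used to define optimal cut-off values for distinguishing pneumococcal disease from carriage", and "Area under the curve (AUC) values will quantify diagnostic performance". It does not name the optimality criterion. Its one outside reference is: "Findings will be cross-referenced with previously published UK datasets to support broader applicability".

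Section 1.4.2 gives the purpose of the revised thresholds: "to support field evaluations and inform diagnostic and surveillance strategies in Malawi and similar settings". Section 1.1 describes the need as "context-specific data to define serotype-specific thresholds that can accurately differentiate carriage from disease", and section 1.0 states: "The current version of ssUAD targets 24 pneumococcal serotypes". On numbers, section 2.6 says "we plan to test all 350 urine specimens collected under the parent NP Resistome study", without giving the split between cases and controls.

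**The concern.** A cut-off that maximises a criterion in one sample is fitted partly to that sample's noise. If its accuracy is then read from the same children, the figure is too favourable on average.

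Nothing else in the protocol fills this gap:

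- The UK cross-reference is offered for applicability. Section 1.0 describes the UK performance data as coming from adults. Section 1.1 says colonisation is uncommon in adults and less likely to interfere, which is why new thresholds are wanted.
- The pilot validation runs in section 7.3 concern the reliability of the assay, not the cut-offs.
- Section 2.3 rules out new recruitment or sampling, so a fresh validation set is not planned.

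At stake is which cut-offs go forward. Flattering figures could make a weak cut-off look usable, and the error is largest for the serotypes with fewest cases.

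**Working it through.** **Plan's own figure.** The protocol gives no figure for threshold accuracy or its precision, so there is none to reproduce. The sample size in section 2.6 concerns group differences in detection and is not used here.

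**Direction of the bias.** Let J(c) = Se(c) + Sp(c) − 1 be the true value at cut-off c, Ĵ(c) the sample value, ĉ the cut-off maximising Ĵ, and c* the cut-off maximising J. Because ĉ maximises Ĵ, Ĵ(ĉ) ≥ Ĵ(c*). For the fixed c*, E[Ĵ(c*)] = J(c*). And J(c*) ≥ J(ĉ) by definition. Hence E[Ĵ(ĉ)] ≥ J(c*) ≥ E[J(ĉ)]. This needs no distributional assumption; only the size does.

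**Inputs for the size**

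- 350 specimens (section 2.6). *Assumed* split of two thirds cases and one third controls: 350 × 2/3 ≈ 233, and 350 − 233 = 117.
- Minimum case: 49 per group (section 2.6), with the two pneumonia groups pooled: 2 × 49 = 98 cases against 49 controls.
- Sparse serotypes: 5 or 10 cases against 117 controls, *assumed*. For plausibility, section 2.6 expects detection in 70% and 53% of the two case groups, midpoint 61.5%. If each positive child had one serotype and positives were spread evenly over 24, then 233 × 0.615 / 24 ≈ 6 cases per serotype.
- *Assumed*: equal-variance binormal marker with separation d = √2·Φ⁻¹(AUC), true AUC 0.6 to 0.9, and a Youden cut-off.

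**Optimism, mean of Ĵ(ĉ) − J(ĉ), by Monte Carlo**

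| Cases/controls | AUC 0.6 | 0.7 | 0.8 | 0.9 |
|---|---|---|---|---|
| 233/117 | 0.056 | 0.050 | 0.042 | 0.034 |
| 98/49 | 0.091 | 0.080 | 0.068 | 0.057 |
| 10/117 | 0.183 | 0.168 | 0.149 | 0.130 |
| 5/117 | 0.249 | 0.237 | 0.220 | 0.196 |

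With 233/117 this is 1.3 to 2.0 points of sensitivity and 2.1 to 3.6 points of specificity. With 5 or 10 cases nearly all of it falls on sensitivity (for example 0.159 of 0.168 with 10 cases at AUC 0.7).

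**Analytic check at AUC 0.7, 233/117.** d = √2 × 0.5244 = 0.742, so the best attainable J is 2Φ(0.371) − 1 = 0.289. The simulation gave apparent J 0.328 and true J at the chosen cut-off 0.278. The apparent value exceeds the attainable maximum and the true value lies below it, as the inequality requires.

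**Intervals.** Wilson 95% intervals computed as if the cut-off were fixed, at true AUC 0.60 to 0.70 and with 262/88 or 233/117, covered sensitivity 91 to 94% of the time, specificity 88 to 92%, and both together 80 to 84%. Two independent 95% intervals would cover jointly 0.95² ≈ 90%.

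**AUC.** The empirical AUC uses all case-control pairs and no cut-off. Its mean was within about 0.002 of the true value in every setting, so choosing a cut-off does not inflate it.

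**Does resampling help?** A separate run at AUC 0.7, so apparent and true values differ slightly from those above:

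| Cases/controls | Apparent J | True J | Bootstrap-corrected | 10-fold CV |
|---|---|---|---|---|
| 233/117 | 0.327 | 0.279 | 0.292 | 0.279 |
| 98/49 | 0.354 | 0.272 | 0.297 | 0.272 |
| 20/117 | 0.384 | 0.263 | 0.306 | 0.267 |

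The bootstrap removes (0.327 − 0.292)/(0.327 − 0.279) = 73% of the bias in the first row and (0.384 − 0.306)/(0.384 − 0.263) = 64% in the last. Cross-validation removes nearly all of it.

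**The case against.** The strongest reply is that section 2.8.3 promises only AUC, which this bias does not touch, and never says that sensitivity or specificity at the new cut-offs will be reported. A reader might infer that the plan's stated accuracy measure will be too high. The text does not support that: single-marker AUC stays unbiased. It would be inflated only if the best-looking serotypes were selected or a multi-marker score were fitted, and the protocol describes neither. The bias is therefore conditional on quoting accuracy at a cut-off. That is still the natural reading. Section 1.3 hypothesises high sensitivity, section 1.4.1 sets out to evaluate performance, and section 1.0 uses a UK sensitivity of 96.2% and specificity of 89.9% as background. It also means that the one named measure does not assess what objective 3 produces.

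Second, resampling detail is often left to a statistical analysis plan, which is not shown here and might supply it. That stands as a caution. The point rests on the derivation method that the protocol does fix.

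Third, the thresholds are partly meant for later field evaluation, and the correction can be made on the same data at any time before reporting. Both are true and both lower the severity. But section 1.4.2 also has the thresholds inform diagnostic and surveillance strategy.

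Fourth, the Youden rule, group split, marker shape and cases per serotype are all assumed. That limits the size, not the direction.

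**Conclusion.** The point holds in a limited form: the protocol derives cut-offs and describes no assessment of them on data not used to choose them. Sensitivity, specificity or J quoted at those cut-offs from the same children would be optimistic, and fixed-cut-off intervals would be too narrow.

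For one pooled cut-off on all 350 children the effect is modest. It becomes large only if serotype-specific cut-offs rest on a handful of cases each. A different optimality rule or marker distribution would change these sizes.

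This should be fixed, but it does not invalidate the study. A reader might also infer that the 214 earlier specimens mentioned in section 2.6 could serve as a validation set. They all come from hospitalised children and so say nothing about specificity in healthy carriers.

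**What to change.** Add to section 2.8.3, in substance: sensitivity and specificity at the derived cut-offs will be reported after bootstrap optimism correction or repeated cross-validation. The cut-off derivation, and any selection among serotypes, will be repeated within each resample. Confidence intervals will come from the same resampling. Uncorrected values will not be used to recommend a cut-off.

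Where cases for a serotype are few, cross-validation is the better choice on the results above.

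The cost is a little more analysis and slightly less favourable accuracy figures. No new specimens are needed.

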## 2.9. Data sharing:

Data generated from this sub-study will be shared with collaborators under restricted-access data sharing agreements. All shared datasets will be de-identified and used solely for the purposes outlined in this protocol, in accordance with institutional and ethical guidelines.

## 3.0 Quality assurance and control

[figure not shown]
All laboratory analyses will be conducted using standardised protocols at the UK Health Security Agency (UKHSA) and NIHR Nottingham Biomedical Research Centre. Internal quality control (QC) procedures and reproducibility assessments will be implemented throughout the testing process to ensure data integrity and reliability.

## 4.0 Dissemination plan

Study findings will be disseminated through multiple channels, including submission to the College of Medicine Research and Ethics Committee (COMREC), presentations at national conferences, such as the Research Dissemination Conference (RDC), and international scientific conferences, as well as publication in peer-reviewed journals. A summary of findings will also be shared with local stakeholders, including clinical and public health partners in Malawi.

## 5.0 Ethical consideration

The parent NP Resistome study (COMREC reference P.10/24-1200) has obtained ethical approval from all relevant institutional review boards. Written informed consent for participant enrollment will be obtained from parents or guardians. Informed consent will be obtained from the parents or guardians of participants for the testing of stored urine samples (collected as part of the NP Resistome study) using urinary pneumococcal antigen assays, with the assistance of a separate patient information leaflet and informed consent form. All procedures will be conducted in accordance with the approved ethical protocol and institutional research governance policies.

MALAWI LIVERPOOL  
WELLCOME PROGRAMME

KAMUZU  
UNIVERSITY  
OF HEALTH SCIENCES

## 6.0 Participant compensation

Participants in this sub-study will receive no additional compensation beyond what is already provided for participation in the NP Resistome study (COMREC reference P.10/24-1200). All participants in the NP Resistome study receive 17,000 MWK as compensation, which covers all study-related procedures, including urine sample collection.

## 7.0 Project risks and constraints

This sub-study is embedded within the NP Resistome study (COMREC reference P.10/24-1200), which will obtain all relevant ethical approvals and is poised to begin participant recruitment. While leveraging the infrastructure and participant pool of the parent study offers significant advantages, there remain potential risks and constraints specific to the successful implementation of the urinary pneumococcal antigen sub-study.

### 7.1. Dependency on NP Resistome recruitment timeline

[figure not shown]
The sub-study relies on timely and sufficient recruitment within the NP Resistome study (COMREC reference P.10/24-1200) to prospectively collect urine samples from children with pneumonia and healthy controls. Any delays or slower-than-expected enrolment in the parent study could limit the number of available urine specimens. To mitigate this, the sub-study team will maintain close coordination with the NP Resistome field team to ensure that urine collection is integrated into the enrolment process for each eligible participant from the outset.

### 7.2. Difficulty in collecting adequate urine volumes

Obtaining sufficient urine volumes, particularly from young children, may pose practical challenges in both community and hospital settings. Missed collections due to dehydration or discomfort could affect sample availability. To mitigate this, caregivers will be supported by trained staff using child-friendly collection protocols.

### 7.3. Laboratory assay limitations or technical errors

The ssUAD assay, although robust, involves complex multiplex detection that requires strict standardisation and quality control to minimise risks such as batch variability, technical failures, or low signal intensity. All testing will be conducted at the NIHR Nottingham Biomedical Research Centre and UKHSA under validated SOPs, with internal quality control and pilot validation runs to ensure assay reliability prior to full sample processing. While a

MALAWI LIVERPOOL  
WELLCOME PROGRAMME

KAMUZU  
UNIVERSITY  
OF HEALTH SCIENCES

Luminex platform is available locally at MLW, current capacity is limited due to a lack of validated reagents, technical expertise, and established protocols specific to ssUAD testing. Therefore, testing will be performed in UK laboratories with the necessary infrastructure and experience. Plans are underway to build local capacity and eventually introduce and evaluate the assay in Malawi as part of future implementation efforts.

#### 7.4. Interpretation challenges due to high carriage prevalence

In a high-carriage setting like Malawi, interpreting the clinical significance of urinary pneumococcal antigen detection, especially among asymptomatic individuals, may be challenging. If urinary antigen is detected in individuals without pneumococcal carriage, or vice versa, this could complicate efforts to set reliable thresholds for distinguishing disease from carriage. To address this, the sub-study will incorporate detailed nasopharyngeal carriage data and apply ROC curve analysis to refine diagnostic interpretation.

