### **2.8.2. Association with carriage dynamics (objective 2):**

Logistic regression models will be employed to assess the association between urinary antigen detection (the outcome variable) and nasopharyngeal carriage (the predictor), adjusting for potential confounders such as age, antibiotic use, and HIV status. Subgroup analyses will examine the influence of carriage density and serotype co-carriage on antigen detection. Multivariable regression and interaction terms will help explore effect modification.

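### Section 2.8.3 sets disease-versus-carriage cut-offs against healthy children it calls carriers, but controls are not selected on carriage and no swab result enters the ROC

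*Protocol*

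**What the plan says.** Section 2.8.3 is the only place where the ROC analysis and the cut-offs are specified. Signal intensities "will be analysed to compare antigen profiles between cases (pneumonia) and carriers (healthy children"). The ROC curve "will be used to define optimal cut-off values for distinguishing pneumococcal disease from carriage", and "Area under the curve (AUC) values will quantify diagnostic performance". No swab result, carriage density, restriction or stratification is named there.

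The study population list in Section 2.1 defines the controls as healthy community children, with or without recent antibiotic exposure. It sets no carriage requirement, and Section 2.3 adds no selection criteria for the sub-study.

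Carriage enters the analysis in Section 2.8.2: "Logistic regression models will be employed to assess the association between urinary antigen detection (the outcome variable) and nasopharyngeal carriage (the predictor"), with adjustment for confounders. Density appears there too: "Subgroup analyses will examine the influence of carriage density and serotype co-carriage on antigen detection". Nothing in 2.8.2 is carried forward to the cut-offs.

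Section 7.4 warns that antigen without carriage, or carriage without antigen, is a difficulty: "this could complicate efforts to set reliable thresholds for distinguishing disease from carriage". Its answer is that "the sub-study will incorporate detailed nasopharyngeal carriage data and apply ROC curve analysis to refine diagnostic interpretation".

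**The concern.** Objective 3 asks whether antigen level separates disease from carriage. That needs a control arm of children known to carry. Section 2.8.3 uses all healthy children and gives them the name of carriers. Any healthy non-carriers then count towards the specificity of a cut-off that is supposed to hold in carriers.

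The case arm is not described by carriage either. The protocol itself expects carriage to produce urinary antigen (Section 1.3). If carriage differs in frequency or density between the arms, the AUC and the cut-off respond to that difference as well as to disease. The difference could go either way: cases might carry more, or they might carry less (or appear to) after antibiotics. The thresholds are intended for Malawi and similar settings, so they could partly reflect who carries rather than who is ill.

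**Working it through.** The protocol states no target AUC, no ROC sample size and no carriage rate by group, so there is no figure of its own to reproduce. The check is first textual and then illustrative.

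**Text side by side**

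- Purpose in 2.8.3: disease versus carriage.
- Contrast in 2.8.3: clinical pneumonia versus healthy.
- Control definition in 2.1: healthy, no carriage condition.
- Carriage data: used in 2.8.2 with antigen detection as the outcome, and not linked to 2.8.3.
- Remedy in 7.4 for the threshold problem: carriage data and ROC analysis, named together.

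Followed literally, the control arm is a mixture. With control carriage c0, specificity in that arm is c0 × Sp(carriers) + (1 − c0) × Sp(non-carriers). If non-carriers have less antigen, this overstates specificity among carriers, which is the quantity that objective 3 needs.

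**Effect on the AUC (all carriage figures assumed)**

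Let the signal be N(d,1) in carriers and N(0,1) in non-carriers, identical in cases and controls given carriage, so that the assay holds no disease information. With carriage c1 in cases and c0 in controls, and A = Φ(d/√2):

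AUC = 0.5·c1·c0 + 0.5·(1−c1)(1−c0) + c1(1−c0)·A + (1−c1)c0·(1−A), which simplifies to 0.5 + (c1 − c0)(A − 0.5).

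For d = 1, A = Φ(0.707) = 0.760.

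- 80% vs 60%: 0.5 + 0.20 × 0.260 = 0.55
- 80% vs 40%: 0.5 + 0.40 × 0.260 = 0.60
- 60% vs 80%: 0.5 − 0.20 × 0.260 = 0.45
- 50% vs 80%: 0.5 − 0.30 × 0.260 = 0.42
- 80% vs 80%: 0.50

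With d = 2, A = 0.921, and 80% vs 60% gives 0.58.

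**Density alone.** If everyone carries, signal = density + N(0,1) noise, and density (SD 1) is s SD higher in cases, then AUC = Φ(s/2). For s = 0.5 this is 0.60.

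**Masking.** Suppose the true AUC at equal carriage status is 0.75, so δ = √2 × 0.674 = 0.954, and d = 1. A case-control pair with equal status has AUC 0.75. With only the case carrying it is Φ(1.954/√2) = 0.917, and with only the control carrying it is Φ(−0.046/√2) = 0.487. At 50% vs 80% carriage: 0.50 × 0.75 + 0.10 × 0.917 + 0.40 × 0.487 = 0.66. At 80% vs 80%: 0.68 × 0.75 + 0.16 × 0.917 + 0.16 × 0.487 = 0.73.

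**Scale.** The detection rates assumed in Section 2.6 imply a single-cut AUC of (1 + 0.70 − 0.35)/2 = 0.675 for hospitalised versus healthy children, and (1 + 0.53 − 0.35)/2 = 0.59 for health-centre cases versus healthy children. Shifts of 0.05 to 0.10 matter against those values.

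**The case against.** - **Section 7.4 is not contradicted.** A reader might infer that 7.4 promises carriage inside the ROC model and that 2.8.3 breaks the promise. The text does not support that. It joins carriage data and ROC analysis with a plain conjunction, both elements appear in the plan, and the risk it names is discordance between antigen and carriage, not carriage imbalance between the arms. What remains is a missing link: thresholds are set only in 2.8.3, and carriage never reaches them.
- **The word carriers may mean swab-positive controls.** That is possible, but no such restriction is written and 2.1 defines controls without one. Even on that reading, the cases would be unrestricted on carriage.
- **Stratification or adjustment belongs in a statistical analysis plan.** This is fair for technique. It does not cover the comparison itself, which the protocol already fixes and which does not match its stated purpose.
- **The size is assumed.** This stands in full.
- **Full adjustment could mislead.** A reader might conclude that the ROC must be adjusted for carriage status and density throughout. The documents do not support that. Section 1.0 reports that antibiotics cut culture-based detection from 81% to 21%. Take true carriage of 80% in both arms, no disease signal, d = 1, control detection of 81%, and all cases exposed with detection of 21%. Among swab-negatives, true carriers are 0.632/0.832 = 0.760 of cases and 0.152/0.352 = 0.432 of controls. Their AUC is 0.5 + 0.328 × 0.260 = 0.585. Weighted over cases, the adjusted AUC is 0.5 + 0.832 × 0.085 = 0.57, although the unadjusted 0.50 is correct. Density may also lie on the pathway to disease, since Section 1.0 calls carriage a prerequisite for invasive disease. This objection stands and limits the remedy.

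**Conclusion.** The point holds in limited form. The ROC in 2.8.3 compares pneumonia with health, while its cut-offs are described as separating disease from carriage. The carrier label is not backed by any swab criterion, and the carriage data that 7.4 offers for this problem are not linked to the cut-offs.

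The mismatch in the text rests on no assumption. The size does. A 20-point difference in carriage moves an uninformative assay to an AUC of about 0.55 or 0.45 when carriers sit 1 SD higher, and lower carriage in cases can hide real discrimination. With no disease signal and equal carriage and density, the AUC shift is nil. A reader might infer that the planned AUC will be inflated; the documents establish neither the direction nor the presence of a difference. The change should be made before the cut-offs are derived, and it needs no new samples.

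**What to change.** In Section 2.8.3:

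1. Define carriers by the nasopharyngeal swab, using both the culture and the metagenomic results that the Executive Summary already plans, not culture alone.
2. Base the carriage-versus-disease cut-off on a ROC with swab-positive healthy children as controls. Report it for all cases and for swab-positive cases. Both are needed: in the model above, with 80% case carriage and no disease signal, the all-cases curve gives 0.5 + (0.80 − 1) × 0.260 = 0.45, while the carriers-only curve gives 0.50.
3. Show the unrestricted pneumonia-versus-healthy curve alongside, under that name.
4. Show results by prior antibiotic exposure, which the parent study records at recruitment.
5. Treat any adjustment for carriage density as a sensitivity analysis only.
6. Refer from 7.4 to this analysis, so that the stated mitigation and the ROC are linked.

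The cost is protocol wording and a few extra curves from data already planned. Two downsides should be stated: fewer children and so wider intervals, and the loss from the swab-positive curve of antibiotic-treated cases whose carriage was missed.
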